Once data entry in MeTree is complete all participants will receive a personalized patient report within the platform outlining their familial and genetic risk status the included medical conditions according to current evidence-based guidelines. Participants' providers will be notified via one of several methods (email without PHI, EPIC messaging, or an alert) that their patient has a MeTree clinical decision support report available in the medical chart (accessible via a SMART link). Outside providers will receive an email or letter. The templates for these messages is located in Appendix I. The process to upload the MeTree report and provide accessibility to providers is approved by the Medical Forms Committee and the Center for Health Information Management (CHIM) Committee.

As previously stated, in Aim 2 participants who are identified as at high genetic risk (n=300) will be contacted by the study nurse (as part of their standard of care) to schedule a genetic counseling appointment (Appendix J, High risk patient email). The number and length of genetic counseling appointments will be recorded in order to evaluate the change in clinic capacity for those with a pre-recorded FHH in the MeTree platform as compared to routine patients who have not participated in the study and completed MeTree. The frequency of genetic testing and outcomes of the testing will also be recorded in REDCap from data collection in the Hereditary Cancer Clinic at VUMC.

[figure not shown]
To analyze the time saved by completing MeTree prior to a clinic visit, the study team will perform a retrospective review of control patients, selected by the study team, to assess the amount of time in clinic with the genetic counselors. This will be done through time stamps in eStar and chart review. Control patients will not be a part of the study, nor will their information be shared with anyone. The study team will only review for time spent in clinic versus the study participants' clinic visits.

Additionally, genetic counselors who see participants from this study will be surveyed to better understand their perspective of the use of MeTree. This portion of the study will be in a separate IRB.

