We will use a case-control design for statistically analyses. Cases are defined as the study participants who have completed the MeTree tool (intervention). We will utilize data from the Hereditary Cancer Clinic registry (IRB # 141203) to fine patients identified at risk of a hereditary cancer syndrome in the usual care (control) and intervention conditions. The control condition utilizes historical data from the participants prior to their enrollment date in FOREST to determine the number and proportion of participants who would be identifiable as at risk without the implementation of MeTree. We believe this is the most effective method to analyze the MeTree platform's effect on hereditary cancer testing and outcomes. Power calculations estimate a sample size of up to 3,500 (minimum of 3,000) is needed to produce statistically significant results.

In the graph below, the blue line represents 90% power to detect the primary endpoint with a p-value of 0.05, the green line, 85% power, and the red, 80% power. The x-axis represents how many participants are identified as being at high risk by MeTree.

In prior studies of primary care populations, on average 20% were newly found to be at high risk (had not previously identified). However, in order to accommodate differences in a population that has a proactive hereditary cancer clinic, we used a lower estimate of 10% for the power analyses. Thus at 10% risk identification and 95% power we estimated that we would need at a minimum 1,000 participants for a single site and 2,000 participants total to detect differences in identification at the 2 sites (Meharry and Vanderbilt). In addition, these participants flow into aim 2. Based on power analysis to detect an increase in clinic capacity, we need to have 150 high risk patients who complete MeTree in Aim 1 to see a genetic counselor in the hereditary cancer clinic at Vanderbilt. At a 10% identification rate and a 50% follow up rate (estimate based on literature review and the clinic's attendance rate), a minimum of 3,000 participants will need to complete MeTree in Aim 1. We are therefore enrolling 3,000-3,500 participants for this study.

Data elements considered for this analysis:

Primary Endpoint: Participant designated as high risk for cancer.

Assessment pre: chart review (any indicator prior to MeTree, not time-frame dependent)

Assessment post: MeTree report (measured when the report is generated, independent of amount of follow-up time)

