Hypothesis: MeTree will increase the proportion of high-risk individuals identified.

Statistical interpretation of the hypothesis: P(of high risk) is a function of the intervention

9. Privacy/Confidentiality Issues

The study data live in a REDCap database. *This project will utilize the REDCap platform for data collection and management. Project team members listed as Key Study Personnel with existing electronic health record (EHR) system access rights may also be granted use of REDCap Clinical Data Interoperability Services (CDIS) tools. These tools are designed to enable transfer of relevant study-related data from the Vanderbilt Research Derivative and/or directly from the EHR into REDCap.*

Participant answers to the survey are linked only to a study ID number in a password protected electronic database. Only study staff will have access to the information, and any paper records are kept in a locked drawer in the study manager's desk. Pragmatic studies are considered minimal risk. All data will be gathered and stored using protocols and privacy & security standards that comply with HIPAA and, where applicable, GINA. All patient FHH data will be gathered from patient portal applications and transmitted to and from the algorithm and clinical decision support databases using industry standard encryption protocols, including HTTPS and TLS. The healthcare systems employ additional protections for the data, including detailed audit logs, insulation from direct SQL queries, and detailed version control.

[name]
U01-CA232829-01A1
FOREST

While participant data such as demographics are collected from the VUMC Epic instance, data are delivered by SFTP to the MeTree platform, housed at Duke University, for participants to complete the FHH questionnaire. FHH results will be transmitted by API to a secure REDCap project at VUMC or MMC. *

*This process is approved by the VUMC Architecture Review Board.

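### Protocol Section 8 compares MeTree's own flag with any chart indicator, so a higher rate shows more flags but not, by itself, more true high-risk people found

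*Protocol*

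**What the plan says.** Protocol Section 8 (Statistical Considerations) sets the endpoint as "Primary Endpoint: Participant designated as high risk for cancer". The before side is "Assessment pre: chart review (any indicator prior to MeTree, not time-frame dependent". The after side is "Assessment post: MeTree report (measured when the report is generated, independent of amount of follow-up time". The claim to be tested is "MeTree will increase the proportion of high-risk individuals identified", and its statistical form is "Statistical interpretation of the hypothesis: P(of high risk) is a function of the intervention". The comparison is within person: "The control condition utilizes historical data from the participants prior to their enrollment date in FOREST". Section 8 gives alpha as 0.05, assumes 10% identification and names no test for this comparison. It also names the Hereditary Cancer Clinic registry as a source for finding patients identified as at risk, in both conditions.

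Protocol Section 5 (Study Procedures) says of the high-risk participants referred to the clinic: "The frequency of genetic testing and outcomes of the testing will also be recorded in REDCap". Section 8 does not use these results.

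The SAP differs. Its primary outcome is completion of MeTree, reported without inference (SAP III.1 and IV.2). Identification is a secondary endpoint: Variable 7, a personal or family history code in the EHR, defined identically before and after consent and compared by McNemar's test (SAP III.2 and IV.3).

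**The concern.** The hypothesis is about high-risk people being identified, but the Section 8 rule counts designations. Each participant contributes two inputs: whether the chart holds any indicator, and whether MeTree raised a flag. The second is the intervention's output at the moment it appears, and it follows a different rule from the first. Neither is checked against common criteria, an adjudication or a test result.

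The direction of the result is then set by how liberal MeTree's threshold is compared with how common chart indicators are. A significant rise could mean that missed people were found, or that more people were flagged. A fall could mean a poor tool, or broad chart coding. A claim of improved identification would not follow from this comparison alone.

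**Working it through.** **The plan's own figure.** Section 8 needs 150 counselled patients, at 10% identification and 50% follow-up: 150 / (0.10 × 0.50) = 3,000. This reproduces. The 1,000 per site at 95% power cannot be checked because no chart rate is stated. With a two-sided test of two independent proportions, a chart rate of about 5.7% would give 1,014. All of these inputs are designation rates; none concerns the accuracy of a flag.

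**Illustration 1: a flag with no information.** Assumptions: MeTree flags a gross 10% independently of the chart, a proportion c has a chart indicator, and a paired two-sided McNemar test at 0.05 is used (borrowed from the SAP's paired analysis).

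- MeTree only: p10 = 0.10 × (1 − c). Chart only: p01 = 0.90 × c.
- d = p10 − p01 and s = p10 + p01.
- Chance of concluding an increase = Φ[(d√N − 1.96√s) / √(s − d²)].

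At c = 8% and N = 3,000: p10 = 0.092, p01 = 0.072, d = 0.020, s = 0.164. The chance is Φ[(1.095 − 0.794) / 0.404] = Φ(0.746) = 77%.

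| Chart rate c (assumed) | N = 3,000 | N = 1,000 |
|---|---|---|
| 5% | about 100% | 99% |
| 7% | 99% | 67% |
| 8% | 77% | 35% |

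**Illustration 2: flag rates against true yield.** Assumptions: N = 3,000, true high-risk prevalence 5% (150 people), chart sensitivity 50% (75 found), and chart and MeTree independent given true status. Here z = d√N / √s.

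- *Over-flagging.* MeTree flags 10% at random and the chart's false-positive rate is 2.5%. Rates are 10.0% against 4.9%, p10 = 0.0951, p01 = 0.0439, z = +7.5. MeTree finds 15 of the 150; the chart finds 75.
- *Loose chart coding.* MeTree has 90% sensitivity and a 3% false-positive rate; the chart's false-positive rate is 15%. Rates are 7.4% against 16.8%, p10 = 0.0467, p01 = 0.1407, z = −11.9. MeTree finds 135 of the 150; the chart finds 75.

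Varying prevalence from 3% to 8% moves z from +9.2 to +5.2 in the first case and from −13.5 to −9.7 in the second. The sign can thus run opposite to the number of true cases found.

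**If the 10% means newly identified.** Section 8 derives its 10% from a 20% figure for people newly found. Read that way, p10 = 0.10. With chart-only rates of 2% to 10%, z at 3,000 runs from 0.08 × 54.77 / √0.12 = +12.6 down to 0. Illustration 1 then no longer describes the protocol's assumption, but accuracy is still absent from the rule. If the after state were taken as chart or MeTree, the proportion could never fall and any new flag would raise it.

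**The case against.** The strongest reply is that high risk here means meeting guideline criteria. Section 5 says the report follows current evidence-based guidelines, so applying them to a collected family history may be what identification means, and a random flag is not a realistic tool. Much of this stands: the illustrations show what the rule cannot exclude, not how MeTree performs. It does not close the gap. The chart side is not held to the same guideline rule, and the flag rests on patient-entered history. The protocol also foresees that an updated report could change high-risk status (Section 5), and that answers to the sex question could lead to inappropriate recommendations (Section 11, subproject Section 6).

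The SAP is a second reply, and it limits the point. It applies one variable to both periods, so neither the mismatch of criteria nor the own-output problem carries over to it. It also supplies no truth standard, and the two documents still disagree on what is primary.

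A reader might infer three stronger things that the documents do not support:

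- *That MeTree over-flags.* No accuracy figure for either side is given.
- *That even a perfect tool would wrongly fail.* If the chart already marked every true case, MeTree would identify nobody new, and not confirming an increase would be correct. Only a label of decreased identification would mislead.
- *That clinic confirmation could replace the endpoint.* Section 5 lists appointment number and length, testing and test outcomes, but not a counsellor's judgement that criteria are met. Such a judgement would probably reuse the same MeTree pedigree. The registry is named for finding patients identified as at risk, not for verifying flags.

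**Conclusion.** The point holds for the protocol's Section 8 comparison and is confined to it. As defined, that comparison estimates a difference in designation rates under two different rules. A significant difference does not by itself support the claim that more true high-risk people were identified.

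The conclusion rests on the endpoint definition. The sizes rest on assumptions: a gross 10% flag rate, a McNemar test that Section 8 does not name, and chart rates, sensitivities and false-positive rates that the documents do not give. Under the first illustration, an uninformative flag would be credited with an increase in about 100% of trials at 5% chart prevalence and 77% at 8%, with 3,000 completers. The point should be corrected because it changes what the trial may conclude; it does not invalidate the SAP's planned analyses.

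**What to change.** 1. Reconcile Protocol Section 8 with the SAP: state which endpoint is primary, which identification endpoint applies, how each side is measured and which test is used. State also whether the 10% is a gross or a newly identified rate.
2. Label the Section 8 comparison *flagged by MeTree versus marked in chart*, and draw no claim of improved identification of true high-risk people from it alone.
3. Report the paired two-by-two table of chart indicator by MeTree flag, including the proportion flagged and not previously marked, with a 95% CI. SAP II.3 restricts EHR-related analyses to VUMC, so say whether the table covers both sites.
4. For flagged VUMC participants, report the chain flagged / not previously marked / seen / tested / test result, with 95% CIs, from the testing data that Section 5 already records.

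The cost is wording plus two tables. With the planned 150 attenders, the 95% half-width of a proportion is at most 1.96 × √(0.25/150) = 0.080, about 8 points. The chain covers only VUMC attenders (a planned 50% of those flagged), checks no chart indicators and does not estimate sensitivity. It should therefore be descriptive support and not a replacement primary endpoint.

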Automated processes are increasingly utilized throughout the healthcare field and research. These automated processes often rely on the electronic health/medical record (EHR/EMR) and/or demographic information obtained from patients. Due to the increased use of automated processes, it is critical that gender identity information is not only documented, but documented accurately to avoid harm to individuals, such as misgendering participants. The failure to identify transgender patients can lead to improper care of patients. Many patients alter their originally recorded legal sex to match their gender identity. For example, if someone changed their sex on their identifying documents from female to male they may be identified within the EMR system as male. Even for patients who do not change their legal documentation, organs and tissues change when participants undergo transition-related medical care, so these patients may have tissues that are not associated with their documentation (e.g., transgender women with breast tissue who still have a legal sex of male). Automated processes that drive reminders for important screening methods for ovaries, uterus, breast tissue, cervix, and other organs and tissues could be missed, thus increasing this individual's risk of illness or disease.

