The Family History and Cancer Risk Study (FOREST) is evaluating an automated hereditary cancer risk assessment (MeTree) with referral to genetic counseling for those deemed to be "high risk" for a hereditary cancer syndrome. Evaluations of the responses from already enrolled transgender and non-binary participants within the FOREST study show that the SGM utilized were interpreted differently by participants. For example, the FOREST question about sex was sometimes interpreted to be asking about a person's sex assigned at birth, while other times it was interpreted as representing gender identity. Because the MeTree risk calculations rely on sex-related information provided by participants, it is of clinical importance to have valid measures for these variables. These differences in interpretation of the same question demonstrate a critical need for redesign and standardization of SGM for research studies and clinical care, especially as relates to genetics care, which requires knowledge of both sex assigned at birth (for risk algorithms), and detailed information about phenotypic sex, hormonal milieu (mixture of endogenous and exogenous hormones), and past procedures (e.g., organ removal) to inform appropriate genetic risk management. For example, a

person who is receiving gender-affirming surgeries or hormone care may need screenings not often provided for those of their assigned sex at birth (ASAB; e.g., mammograms are not typically provided for people assigned male at birth, but may need to be provided for transgender women and other people assigned male at birth who develop breast tissue from exogenous gender-affirming hormone therapy). Similarly, knowledge of hereditary cancer risk can inform choice of surgical procedure for chest reconstruction for patients seeking breast tissue removal and inform needed screenings for patients who have already had this procedure. As a result, routine family history risk assessment is a critical component of transgender care – but unfortunately, this component is often overlooked.

2. Rationale & Specific Aims

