To reduce potential harms, thoughtful and inclusive standardized SGM and guidelines for ethical data collection and usage need to be developed in collaboration with members of the transgender, gender- and sex- diverse (TGSD) communities. We have chosen the terminology TGSD to broadly encompass a subset of individuals from the NIH Sexual and Gender Minorities definition, those 1) who are transgender, non-binary, or intersex, 2) whose gender identity does not align with their sex assigned at birth, 3) who have a difference of sex development, or 4) whose gender identity or expression, or reproductive development is characterized by non-binary constructs of gender and/or sex. To this end, we plan to conduct semi-structured interviews with TGSD individuals who participated in the FOREST study to understand their interpretations of the SGM used. Additionally, we aim to evaluate the potential clinical and psychosocial harms associated with use of various SGM data models used in genetics, including that used in FOREST. We will obtain participant's advice for improving upon the MeTree SGM and guidance on usage of this data in automated systems. This information will be used to provide recommendations for the thoughtful and inclusive standardization of those questions for future genetics studies and in genetics clinical care. We hypothesize that in semi-structured interviews participants will elucidate gaps in the MeTree and FOREST SGM, reveal potential social and clinical harms associated with current models, and provide recommendations for designing thoughtful and inclusive SGM. These recommendations for SGM will provide greater validity for incorporation into automated care processes. In semi-structured interviews we will:

Aim 1. Explore TGSD participants' interpretation of SGM used in the FOREST study to assess measure validity.

We will evaluate TGSD participants' interpretation of SGM used in the FOREST study, as well as alternative question/response formats from the literature. These descriptive evaluations will provide insight into the validity of sex- and gender-related question/response structure used in FOREST as well as alternative formats.

Aim 2. Evaluate the psychosocial and clinical impact of SGM on TGSD participants and assess harms.

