- Identified via the EHR (using diagnosis, procedure, or billing codes or gender identity/sex assigned at birth data) to be TGSD, or identified via responses on the FOREST survey or the MeTree family history application with a response consistent with being TGSD, or responses on MeTree that they prefer not to disclose a gender identity or do not know their sex assigned at birth ("Unknown"). Note that FOREST consented participants have already consented to the use of FOREST-collected data and their EHR data by the main study.
 - The following response selections on FOREST and MeTree will be considered eligibility criteria for recruitment to interview: "Other" for the FOREST survey question of "Sex"; "Other" or "Unknown" for the MeTree question of "Birth sex"; "Non-binary," "Transgender male-to-female," "Transgender female-to-male," "Other," "Unknown" or "Prefer not to respond" for the MeTree question of gender identity. Further, we will also include FOREST participants who have any discordant responses amongst these three questions (e.g., those who respond "female" to birth sex and "male" to gender identity), or have an inconsistency between their legal sex in the EHR and their sex assigned at birth in the EHR or their reported FOREST data. We will also include FOREST participants who have EHR diagnosis codes consistent with TGSD identities or receiving gender-affirming care.
 - Because not all FOREST participants have completed MeTree, we will also use a predefined set of EHR-coded data to identify other TGSD participants among enrolled

FOREST participants. These codes have been previously validated in another study (Bick et al., in preparation).

- Must consent to participate in a recorded and transcribed qualitative interview for formal study analysis

3.2. Exclusion:

- Not a FOREST participant
- Does not meet substudy definition of TGSD described above
- Does not consent to recorded interview

4. Enrollment

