Recruitment will begin after the substudy has been approved by the IRB and will occur on a rolling basis as individuals who meet eligibility criteria are added to the main FOREST study. Invitations will be sent via email to FOREST participants who meet the substudy eligibility criteria defined above. Follow-up phone call(s) will occur to email non-respondents to enroll participants. Attempts will be made to reach participants up to four times by phone/email. Participants who respond favorably to email or phone within that time will have follow-up communication regarding scheduling for a follow-up semi-structured interview. To ensure that we have a large enough pool of eligible FOREST participants who meet eligibility criteria for this substudy, we will also enhance FOREST recruitment efforts in clinic and community areas that reach VUMC TGSD patients. For this we will distribute FOREST recruitment materials in the adult transgender clinic at VUMC and to LGBTQ+ community interest groups (both online and in person) in the greater Nashville area. In both recruitment avenues, we will tailor recruitment materials (see documentation included in the amendment) to inform TGSD adults of the relevance of hereditary cancer risk assessment to their health care and to acknowledge that we are interested in enrolling TGSD participants for additional interviews about how to make the study more inclusive. These additional materials, as well as all materials associated with this substudy, were designed with the oversight of [name] and [name], two transgender members of the FOREST research team.

Participants who agree to be interviewed in the substudy will either be allowed to use the web conference link to secure software or will be phoned out from secure software, based on participant preference at the time of their scheduled interview. We will use a secure Microsoft Teams web conference or Microsoft Teams web conference phone call; Microsoft Teams is VUMC-approved secure software for this purpose. Prior to the interview, we will send the participant the eConsent link. They can choose to read and sign before the interview or go through the consent with the interviewer on the phone. Before the interview begins, the interviewer will confirm that the consent is signed and if the participant has any questions.

5. Study Procedures

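### Interview-substudy eligibility uses only recorded answers and EHR data, so a TGSD participant whose answers and records all agree has no way in

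*Protocol*

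**What the plan says.** All references are to the substudy, Protocol Section 11, and its own subsection numbers. The SAP does not deal with the substudy.

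- **Definition (Section 2).** The plan says: "We have chosen the terminology TGSD to broadly encompass a subset of individuals from the NIH Sexual and Gender Minorities definition". The four-part definition covers people "who are transgender, non-binary, or intersex", people whose gender identity differs from sex assigned at birth, people with a difference of sex development, and people described by non-binary constructs of gender or sex.
- **Purpose (Section 2, Aim 1).** "Explore TGSD participants' interpretation of SGM used in the FOREST study to assess measure validity". SGM are the sex- and gender-related measures.
- **Eligibility (Section 3.1).** A FOREST participant qualifies through EHR codes or EHR gender identity or birth-sex data, or through listed answers to three items (FOREST sex, MeTree birth sex, MeTree gender identity). A mismatch among the three items also qualifies ("we will also include FOREST participants who have any discordant responses amongst these three questions"), as does legal sex in the EHR that disagrees with EHR birth sex or with the FOREST data. Non-disclosure is admitted on purpose: "or responses on MeTree that they prefer not to disclose a gender identity or do not know their sex assigned at birth".
- **Exclusion (Section 3.2).** Anyone outside the substudy's TGSD definition is excluded. The text does not say whether that means the Section 2 concept or the Section 3.1 rule.
- **Invitation and outreach (Section 4).** Invitations go to those who meet the criteria. Materials for the transgender clinic and community groups will "acknowledge that we are interested in enrolling TGSD participants for additional interviews about how to make the study more inclusive".

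**The concern.** The target population is defined by who people are, but entry depends on what their answers and records show. The two differ for a TGSD person whose recorded data all point the same way.

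This matters more here than in most interview studies because the items under examination also do the selecting. Section 1 reports that the FOREST sex question was read by some as sex assigned at birth, "while other times it was interpreted as representing gender identity". If a person's reading makes all three answers agree, the survey raises no flag. The legal-sex check can be silent as well, since the protocol itself notes: "Many patients alter their originally recorded legal sex to match their gender identity".

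What is at stake is the range of experience that reaches the interviews. Section 1 says MeTree's risk calculations rely on the sex answers, and Section 2 says the results will shape updated MeTree measures. A way of reading the items that leaves no trace in the data is one the substudy would want to hear about, and the rule cannot find it.

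**Working it through.** The substudy states no sample size, prevalence or accuracy for its criteria, so there is no planned figure to reproduce. The check is on the logic of the rule.

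**Inputs.** These come from Section 3.1. The plain male and female options are assumed, because the protocol lists only the qualifying answers.

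- FOREST sex: male, female, other (3)
- MeTree birth sex: male, female, other, unknown (4)
- MeTree gender identity: male, female and the six listed options (8)
- EHR legal sex: male, female (2)
- EHR sex assigned at birth: male, female, not recorded (3)

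**Rule without any EHR code or EHR gender identity entry.** A pattern qualifies if it contains a listed answer, if the three answers disagree, if legal sex differs from EHR birth sex, or if legal sex differs from a reported answer.

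**Counts.**

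- Answers alone: 3 × 4 × 8 = 96 patterns. Two do not qualify (male throughout, female throughout), so 94 do.
- Answers plus EHR fields: 96 × 2 × 3 = 576 patterns. Four do not qualify: male throughout with legal sex male, and female throughout with legal sex female, each with EHR birth sex matching or blank. So 572 do.
- MeTree not completed: 3 × 2 × 3 = 18 patterns. Four do not qualify, for the same reason.

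These are counts of patterns. They say nothing about how many people fall in each.

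**Who can fall in the unflagged patterns** (no EHR code or gender identity entry):

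| Participant | Eligible? |
|---|---|
| Transgender woman, female throughout, legal sex female, EHR birth sex blank | No |
| Transgender person answering by assigned sex throughout, legal sex unchanged | No |
| Person with a difference of sex development, consistent answers and records | No |
| Non-binary person, MeTree not completed, FOREST sex matches EHR | No |
| Transgender woman, female throughout, legal sex male | Yes |
| Transgender woman, female throughout, legal sex female, EHR birth sex male | Yes |
| Transgender woman, FOREST sex female, birth sex male, gender identity female | Yes |

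**Following the first four through recruitment.** Section 4 invites only people who meet the criteria. Section 5 explains the topic to those already contacted. Neither describes how an uncontacted FOREST participant could come forward. Someone who joins FOREST because of the Section 4 outreach and then answers consistently, with no EHR flag, remains ineligible.

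**Can a direction of bias be derived?** Let m be the share of TGSD participants who misread the items, d the share of misreaders the rule captures, and e the share of the others it captures. The share of misreaders among eligible TGSD people is m·d / (m·d + (1 − m)·e). All values below are assumed:

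- m = 0.3, d = 0.8, e = 1: 0.24 / (0.24 + 0.70) = 26%, below the true 30%.
- m = 0.3, d = 0.8, e = 0.8: 0.24 / (0.24 + 0.56) = 30%, unchanged.
- m = 0.3, d = 0.8, e = 0.6: 0.24 / (0.24 + 0.42) = 36%, above it.

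The documents give none of these rates. Some of those missed, such as intersex people answering consistently or people who did not complete MeTree, need not be misreaders, so e = 1 cannot be taken for granted. The sign is undetermined.

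**The case against.** The strongest reply is that the net is already wide. Section 3.1 combines several routes, the EHR routes work even when the survey answers agree, and the codes are described as validated in another study. To be missed, a person must give three agreeing answers, choose no transgender or non-binary option, and have matching legal sex, no contradicting EHR birth sex, no EHR gender identity entry and no code. That stands, and it is why the point is minor. It does not close the gap, because nothing described lets such a person in.

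A reader might infer more than the documents support:

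- **That the study never asks.** It does. MeTree has a gender identity question with transgender and non-binary options, and choosing one qualifies the person. What is missing is a way to self-identify at substudy recruitment.
- **That misreaders are generally screened out.** Mostly the reverse holds. Someone who reads one item differently from the others becomes discordant and is included. Only readings that leave everything in agreement are lost.
- **That the sample makes the items look better than they are.** The check above shows the sign depends on capture rates that nobody has stated. Admitting every discordant answer could equally over-represent difficulty with the items.
- **That many interviewees will not be TGSD, so status must be confirmed.** A person who declines to answer or mis-enters an item can qualify. But admitting *Unknown* and *Prefer not to respond* is an open choice, and explaining the topic at contact lets people opt out. No prevalence or false-flag rate is given, so no share can be calculated. The interview guide and amendment materials were not available, so a status question there cannot be ruled out. Requiring non-disclosers to disclose, or setting them apart, would cut against their deliberate inclusion and the substudy's privacy safeguards.

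**Conclusion.** The point holds in a narrow form. A FOREST participant can meet the Section 2 definition, have wholly concordant answers and records, and be neither invited nor able to volunteer. Because Aim 1 studies the items that help select its sample, readings that leave no flag are under-covered.

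The substudy codes interviews into themes (Section 8) and estimates no proportion, so the consequence is for the coverage of themes and not for an estimate or an error rate. How many people are affected cannot be found from the documents. The conclusion rests on Sections 3 to 5 being the full description of entry, and on the assumed male and female options. Severity is minor. It is worth acting on because the remedy is cheap.

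**What to change.** 1. **Section 3.1.** Add a route such as: *or self-identifies to the study team as TGSD under the Section 2 definition, whatever the recorded answers.* FOREST enrolment and consent to recording would still be required. The Section 4 outreach materials already name the topic and could mention this route, leaving the deliberately neutral emails and voicemails unchanged.
2. **Section 3.2.** Reword it to exclude only people who meet neither the Section 2 definition nor a Section 3.1 route. This removes the ambiguity and keeps the intended inclusion of *Unknown* and *Prefer not to respond*.
3. **Reporting.** Give the number of interviewees by entry route (listed answer, discordance, EHR data, self-identification), with any self-description they volunteer. No one need be asked to disclose.

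The cost is an IRB wording amendment and a little tracking, which can sit in the REDCap contact record the substudy already uses.
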